individualizing ICP/ CPP treatment with the use of ICP indices such as autoregulation and PrX, the relationship between this parameter and variables of ventilator mechanics needs elucidation^{20,25}. In addition, the associations between MV and brain oxygenation and cerebral blood flow, all need further investigation.

Expected benefit

Better understanding of the influence of MV on multimodal neuromonitoring parameters might provide evidence for the best MV strategy to guide the clinical management of brain injury, while avoiding respiratory complications that may delay recovery and start of rehabilitation. The data gained by this project might lead to new treatment recommendations for patients with ABI focusing on outcome measures such as safety and effectiveness of care. The project will also identify respiratory and cerebral variables that should be included in a national or international multicenter study where the main outcome measures would relate to mortality and number of ICU days. The ICM+ software is a research tool that is used in more than 50 neurosurgery centers worldwide and the ICP curve analysis has gained international recognition. Nevertheless, there is a lack of research on ventilator settings and ICP waveform analysis and this project will be the first to integrate the ventilator parameters in ICM+ and study its clinical use. All centers using ICM+ will be able to use the new integration that will be developed and tested in this project, should it prove to be effective.

Measurement of P_{tp} is a well-recognized research and clinical tool to better manage respiratory failure. But, there is little competence in the use of this method in Norway. We will develop a high level of experience with this methodology, which can then be applied for other patients with respiratory failure and the knowledge can also easily be transferred to other hospitals in Norway.

Study objectives

The proposed study is an exploratory analysis of the relationship between cerebral blood perfusion and oxygenation and lung mechanical variables at different ventilator settings. The primary approach will be to carry out baseline measurements to enable conclusions concerning the safety of PLV on normal ICP before extending the study to patients with more severe brain or lung injury in future studies.

The primary objective of Brain Vent is to investigate if PLV (higher PEEP and lower TV) as compared with conventional settings (lower PEEP and higher TV)

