- Body mass index (BMI) > 35.
- Known right or biventricular cardiac failure with cardiac index < 2,5 L/min/m² or ejection fraction < 40 %.
- Refractory hypovolemia as diagnosed with pulse pressure variation > 12 % with tidal volume 8 ml/predicted bodyweight (intubated on controlled ventilation) or passive leg rise test with > 10 % increase in stroke volume measured by VTI echocardiography or PICCO.
- Medulla lesion that affect the autonomic nervous system.
- Patients who has undergone decompressive craniectomy.

Planned number of participants and statistical analysis

In this study setting, we aim to show that LPV is non-inferior to conventional ventilator setting, with regards to ICP increase or change of PrX > 0.3 (diminished autoregulation).

Sample size calculation is based on the primary outcome and the cross-over study design. Assuming a difference of zero, a standard deviation of 4 mmHg and a non-inferiority margin of 3mmHg, power of 80% and a significance level of 0.025, a total of 28 patients will be included¹⁶. We will recruit 30 patients to Brain Vent to take account of technical issues or dropouts. The non-inferiority margin is chosen to be lower than the minimal clinical important difference of 5 mmHg. It is assumed that there will be no missing data in the period 2 measurements due to the short time interval between the two different interventions. The sample size calculation is done with STATA 15.1 and the main analysis will be done in SPSS.

Descriptive statistics will be presented with mean and standard deviations or median and interquartile range as appropriate for continuous variables. Categorical variables will be presented as proportion of patients in the different categories. Subject level profiles for each group (AB, BA) will be plotted to visualize the results. The hypothesis of non-inferiority will be tested based on the

lower confidence limits of the difference. Period effect, sequence effect and secondary outcomes will be analysed with linear mixed models.

Procedure

Patients will be ventilated with Servo U® ventilators (Maquet, Rastatt, Germany). Treatment will follow local procedures.

Intervention

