PLV include change in two parameters, PEEP and TV. In order to analyse whether a change in TV affects the patient, we will test TV and PEEP changes in two different ventilation protocols, called intervention 1 and intervention 2 (Table 1). One of these will have lower TV, and the other will have lower TV and higher PEEP. We are not testing higher PEEP without lower TV to minimize risk of overdistending the lungs. Baseline is standard ventilator settings as described in Table 1. Each patient will receive the two interventions using a cross-over design, in which they will be randomly allocated to either have intervention 1 first followed by intervention 2, or vice versa. This will boost the power of the analysis because each patient's outcomes on intervention 1 will be compared with her/his outcomes on intervention 2. The basic model, as described in Table 2, is chosen because being a complex ICU patient, within-patient variability in respiration and brain damage is less than between patient variability. Because the patient's study time is short, all patients should reach the second period of their randomization and receive both interventions. Therefore, this is a powerful design in this study setting.

The randomization will be done with dedicated software at the research department of the study hospital and her/his randomized order will be concealed until the patient has entered the study. Subsequently, the analysis will be blinded for which intervention is which. The treatment responsible physician (not the researcher who makes the recordings) will change the ventilator settings in accordance with the randomised order and will interrupt the intervention if ICP rises above 22 over 5 minutes, for safety reasons.

Table 1. Study procedure (for those patients randomly allocated to the intervention 1 followed by intervention 2 sequence. Group A). Group B will have the reverse order with Intervention 2 first.

Procedure Observation time	Baseline (run-in period) 2 h	Intervention 1 1.5 h	Baseline (wash-out) 1,5 h	Intervention 2 1,5 h
PEEP (mmHg)	5	5	5	12
TV (ml/kg PBW)	9	6	9	6

Table 2. The basic design model²⁶. Each patient is treated for 2 periods of time. Patients are randomly allocated to receive treatments in this order (intervention 1 first, followed by intervention 2) or the reverse order (intervention 2 first, followed by intervention 1)

	Group A	Group B
Period 1	Intervention 1	Intervention 2
Period 2	Intervention 2	Intervention 1

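### The primary question is PLV against conventional ventilation, but the cross-over comparison spelled out is Intervention 1 against Intervention 2, and the plan does not define the difference to be tested

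*Combined protocol and SAP*

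**What the plan says.** Under Study objectives, the primary aim is to "investigate if PLV (higher PEEP and lower TV) as compared with conventional settings (lower PEEP and higher TV". The section on planned number of participants and statistical analysis turns this into a hypothesis: "we aim to show that LPV is non-inferior to conventional ventilator setting", with regard to an ICP increase or a "change of PrX > 0.3 (diminished autoregulation". The plan uses PLV and LPV for the same thing. Only Detailed conduct of the study ties the term to a setting, by attaching it to the step with TV 6 and PEEP 12, which is Intervention 2.

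The Intervention section randomises the order of Intervention 1 (TV 6, PEEP 5) and Intervention 2 (TV 6, PEEP 12). It explains the power of the design by saying that each patient's "outcomes on intervention 1 will be compared with her/his outcomes on intervention 2". Table 2 has two periods and two groups, with no cell for conventional ventilation. In Table 1, conventional settings (TV 9, PEEP 5) are the run-in and the wash-out, in the same positions for both groups.

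The analysis text says "Subject level profiles for each group (AB, BA) will be plotted to visualize the results", assumes "no missing data in the period 2 measurements due to the short time interval between the two different interventions", tests non-inferiority on the "lower confidence limits of the difference", and adds that "Period effect, sequence effect and secondary outcomes will be analysed with linear mixed models".

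**The concern.** The question and the described comparison do not match. Intervention 2 against Intervention 1 estimates the effect of PEEP at TV 6. It cannot show that PLV is non-inferior to TV 9 with PEEP 5, because whatever the lower tidal volume does to ICP is in both terms and drops out.

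An analyst who starts from the hypothesis sentence still has to supply three things that the plan leaves open:

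- **Reference.** Run-in, wash-out or both could be the conventional value.
- **Sign.** Higher ICP is worse, so a lower limit is the right one only if the difference is conventional minus PLV.
- **Time.** The period and sequence terms fit the two randomised periods. The plan does not say that the mixed model yields the primary difference, or how the fixed conventional segments enter it.

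The result is meant to support a statement on the safety of PLV before the work is extended to sicker patients, so an undefined primary contrast matters.

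**Working it through.** **1. The plan's own figure.** Inputs from the statistical section: difference 0, SD 4 mmHg, margin 3 mmHg, power 80%, significance level 0.025 (taken as one-sided). If 4 mmHg is the within-patient SD, the variance of a difference between two single segments is 2 × 16, and

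N = 2 × 16 × (1.960 + 0.842)² / 9 = 27.9, so 28.

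This reproduces the stated 28. Had 4 mmHg been the SD of the paired difference, N would be 14; the within-patient reading is therefore inferred. The same 28 results for Intervention 2 minus Intervention 1, minus run-in or minus wash-out, so the sample size does not reveal which contrast was meant.

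**2. Testing Intervention 2 minus Intervention 1.** SE = 4 × √2 / √28 = 1.069 mmHg. Let D1 and D2 be the effects of Interventions 1 and 2 over conventional, and set D2 = 3 (harm at the margin). The tested difference is 3 − D1, and the chance that its upper limit lies below 3 is Φ(D1 / 1.069 − 1.96). D1 is assumed; the documents give no value.

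| Assumed D1 (mmHg) | Normal | t-based |
|---|---|---|
| 0 | 2.5% | 2.5% |
| 1 | 15% | 14% |
| 2 | 46% | 44% |
| 3 | 80% | 77% |

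**3. Sign.** If the difference is PLV minus conventional and its lower limit is compared with −3, the chance of passing at a true harm of 3 mmHg is Φ((3 + 3) / 1.069 − 1.96) = Φ(3.65), over 99.9%. With the upper limit against +3 it is 2.5%.

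**4. Reference segment and drift.** Table 1 durations (2, 1.5, 1.5 and 1.5 h) put segment midpoints at 1, 2.75, 4.25 and 5.75 h. With equal groups, Intervention 2 is centred on (2.75 + 5.75) / 2 = 4.25 h. Its mean lag behind conventional is:

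- run-in: 4.25 − 1 = 3.25 h;
- mean of both: 4.25 − (1 + 4.25) / 2 = 1.625 h;
- wash-out: 4.25 − 4.25 = 0 h.

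These lags are the bias in mmHg per 1 mmHg/h of common linear drift. A model with a linear time term also has zero bias. At an assumed 0.25 to 0.5 mmHg/h the bias is 0.8 to 1.6 mmHg (run-in), 0.4 to 0.8 mmHg (mean of both) or 0 (wash-out), against a 3 mmHg margin. Falling ICP favours non-inferiority; rising ICP works against it. The section on observations has ICM+ recording 3 h at the start setting. If the run-in were that long, the mean-of-both figure would be 1.875 rather than 1.625.

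**5. Carry-over.** The wash-out follows Intervention 1 in Group A and Intervention 2 in Group B. If a fraction c of each effect persists through it, the mean wash-out value rises by 0.5c(D1 + D2), and Intervention 2 minus conventional shifts by:

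- −0.5c(D1 + D2) with the wash-out as reference;
- −0.385c(D1 + D2) with all four segments and linear time;
- −0.25c(D1 + D2) with both conventional segments and no time term.

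For example, with D2 = 3 and c = 0.25 (both assumed), the wash-out-only shift is −0.375 mmHg if D1 = 0 and −0.75 mmHg if D1 = 3. Positive carry-over of harm favours non-inferiority.

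**6. Precision of two workable analyses (n=28, true difference 0, independent errors).** Wash-out reference: SE 1.069, power 77% (t) to 80% (normal). Four segments with patient, three-level setting and linear elapsed time: SE 1.006, power about 84%; adding sequence does not change the contrast.

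**The case against.** The intent is fairly clear. The hypothesis sentence names LPV against conventional, and Detailed conduct labels TV 6 with PEEP 12 accordingly. The Intervention section also says that the two protocols are there to learn whether changing TV matters; since both use TV 6, only a comparison with conventional can answer that. The sentence about comparing the two interventions gives a reason for the design and is not an analysis specification. The AB/BA plots and the period 2 remark are compatible with four-segment data. All of this stands, and it makes Intervention 2 against conventional the natural reading. It does not supply the reference segment, the sign or the time handling.

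Four stronger readings are tempting but unsupported:

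- **The trial cannot answer its primary question.** Every patient is due to have conventional segments recorded, so the contrast can be estimated.
- **Intervention 2 minus conventional is not estimable.** That is true only if all four time slots have free effects, a model the plan does not propose.
- **The lower limit is an error.** It is correct for conventional minus PLV; the plan does not say which way it subtracts.
- **The sample size is wrong.** It reproduces.

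Nor do the documents show that drift or carry-over occurs. Those figures describe exposure under assumed values.

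**Conclusion.** The point holds as a failure to define the primary contrast. The mismatch between question and described comparison, and the open sign, follow from the text and need no assumption. Their size is conditional. False non-inferiority from testing the two interventions against each other runs from 2.5% to about 80% over assumed Intervention 1 effects of 0 to 3 mmHg, given n=28 and an inferred within-patient SD of 4 mmHg. The wrong pairing of sign and limit would leave almost no protection.

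The choice of reference trades one exposure for another. Run-in is open to drift, wash-out to carry-over in both sequences, and using both without a time term to some of each. Randomised order protects this contrast only in part, since conventional ventilation is never a randomised period. The calculations do not make linear time the one correct model. A wash-out reference is equally defensible, provided that it is named in advance.

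**What to change.** Change the analysis wording as follows, before unblinding.

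1. Name Intervention 2 minus conventional as the primary contrast, and declare non-inferiority if its upper confidence limit is below +3 mmHg.
2. State the reference segment and time handling. Either use the wash-out segment (no linear-drift bias, the precision implied by N=28, largest carry-over exposure), or fit one mixed model to all four segments with patient, three-level setting, sequence and linear elapsed time. Make the other a sensitivity analysis.
3. State the no-carry-over assumption.
4. Use the same contrast for PrX.
5. Say how segments cut short by the stopping rule (ICP above 22, or CPP below 50 mmHg) enter the analysis, so that patients who were harmed are not dropped.
6. Report Intervention 2 minus Intervention 1 as the randomised secondary contrast, labelled as the PEEP effect at TV 6.

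This needs no extra patients, time or measurements. The cost is a little more analysis work and an open statement that randomised order protects the primary contrast only in part.

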Ventilatory settings in detail:

a. Conventional settings- Volume control (VC), inspiratory: expiratory (I:E) ratio 1:2, Tinsp 10 %, PEEP 5 cm H₂O, VT 9 ml/predicted bodyweight, ventilator frequency (Vf) needed to give partial pressure of carbon dioxide (PaCO₂) 4.5-5 kPa, oxygen saturation (SpO₂) > 96. Plateau pressure < 30 cm H₂O

b. Intervention 1- VC, I:E ratio 1:2, Tinsp 10 %, PEEP 5, TV 6 ml/predicted bodyweight, Vf (<30/min) will be increased to the same minute ventilation as in a. Plateau pressure < 30 cm H₂O

c. Intervention 2- VC, I:E ratio 1:2, Tinsp 10 %, PEEP 12, TV 6 ml/PBW, Vf (<30/min) will be increased to the same minute ventilation as in a., SpO₂ > 96. Plateau pressure < 30 cm H₂O

Age (≥ 70 , < 70) and type of damage (TBI or SAB) will be stratified in the two groups in the randomisation.

Observations and outcome measurements during the study:

All primary and secondary outcome measurements will be recorded from minimum 2 hours before to 1 hours after intervention. ICM + will record monitoring signals for 3 h during the start setting for calibration of the PrX signal.

Respiratory component

Respiratory settings and changes will be measured by

- Blood gases: PaO₂/FiO₂ ratio.
- Pressure transducer in esophagus: Esophageal pressure (P_{eso}). Continuously and end-insp/end-exp just.
- Ventilator: Oxygenation index, end-tidal CO₂ (etCO₂), inspiratory oxygen fraction (FiO₂), Peak airway pressure (P_{peak}), P_{plateau}, PEEP, End-expiratory airway pressure (Paw_{Endexp}), Vf, tidal volume inspiratory (VT_{insp}), tidal volume expiratory (VT_{exp}) at each breath, Total PEEP (end expiratory occlusion), from Paw and P_{eso} and hence from P_{tp}.
- Pulse Contour Continuous Cardiac Output (PICCO) thermodilution: Extravascular lung water index (EVLWI) as a determinant of fluids in the lungs.

Cerebral component:

ICP will be measured by:

- Invasive- ICP probe placed intraparenchymal or in the ventricular space
- Non-invasive ICP with transcranial Doppler (TCD) measurement of optic nerve sheath diameter and straight systolic flow velocity or flow velocity of MCA bilaterally.

Intracranial pressure indices, as a measure of compensatory reserve and autoregulation will be assessed by

- Intracranial and arterial pressure waveform analysis with ICM+® - PrX. Compensatory reserve index (RAP) index and mean pulse amplitude (AMP). Slow AMP. See further down for references.

Brain blood perfusion and oxygenation;

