- Brain tissue oxygen tension (PbtO₂). *Only for patients having a clinical indication for CT caput.*
- if clinically indicated.
- TCD measurement of flow velocity in arteria cerebri media.
- Computer tomography (CT) of brain perfusion for assessment of global and local cerebral perfusion during the first 24 h. *Only for patients having a clinical indication for CT caput.*
- Protein S100B is a new outcome prediction tool in brain injury, which is not thoroughly explored²⁷. It will be analysed on admission as part of a description of the severity of ABI.

Cardiovascular component:

Positive pressure ventilation may hamper venous return, which might decrease cardiac index and cerebral blood flow. Therefore, data from the cardiovascular system also will be included.

A PICCO arterial catheter and a central venous catheter will be inserted for continuous measurement of the following intravascular pressures and cardiac index and derived variables by thermodilution once/hour:

- Cardiac output
- Stroke volume
- Arterial blood pressure
- Central venous pressure

- Intrathoracic blood volume index (ITBVI) as determinants of preload.
- The following treatment will be documented:
- Vasopressor dose
 - Inotropic support
- Any fluid transfusion, amount and constitution

Other patient data that will be registered

Background and baseline demographic data of the study population: Sex, Glasgow coma scale before intubation, diagnosis, age, PBW, BMI, type of ICP monitoring, CT Marshall score, extracranial injuries.

In hospital treatment data: Daily fluid administration, duration of invasive and non invasive ventilation, duration and dose of sedation, ICU days, duration of the hospital stay in days from admission to hospital to discharge to home or rehabilitation.

Rationale for choice of monitoring

Cerebral monitoring:

ICP will be measured continuously as part of routine monitoring by invasive ICP probe in the brain. It will also be assessed noninvasively with transcranial Doppler (TCD)²⁸. In the future, non-invasive ICP measurements will most likely be the gold standard. Therefore, it is important to find out if TCD changes reflect changes in ventilator settings as accurate as the invasively measured ICP changes.

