P_{eso} measurement enable calculation of tidal P_{TP}, which is the pressure needed to insufflate the lung¹². It can be determined by measuring the pressure difference in end inspiration and end expiration between airway pressure and intrapleural pressure, represented indirectly by the pressure changes determined in the esophagus. By calculating P_{tp} we will document if there is any relationship between the tidal P_{tp} and monitored cerebral parameters in the different procedures.

Even if we use the same TV and PEEP in lung protective ventilator settings in different patients, there might be a different change in tidal P_{tp} that need to be addressed in future studies.

PICCO monitoring system (Pulsion Medical Systems, Munich, Germany):

A thermistor catheter will be placed in a femoral or brachial artery. PICCO measurement will be used to monitor both preload, cardiac output and changes in EVLW. All these parameters might be affected by the lung protective settings and can be related to cerebral parameters, such as ICP, CPP, ICP indices and cerebral oxygenation and metabolism variables. Increased EVLW has been noticed, on the average, more than two days before the patients meet ARDS criteria³¹. Therefore, we suggest that measurement of EVLW and pulmonary vascular permeability index (PVPI) in ABI patients at risk might enhance our possibilities of diagnosing the condition at the stage of emerging or “mild ARDS”. In addition, determining pre-load by means of changes in intra-thoracic blood volume index (ITBVI), might provide valuable information about fluid load³².

Detailed conduct of the study

Pre- intervention phase:

1. A member of the research team will recruit the patient within the first 24 hours after the ABI after rigorous consideration of the exclusion criteria
2. The patient will receive standard care with deep sedation, fentanyl/propofol and elevated upper body by 20 degrees.
3. Pleural effusion > 2 cm will be excluded with ultrasound.
4. The ventilator settings will be conventional as described above and in Table 1.

Intervention phase with randomized order of intervention 1 and 2:

- a. Intervention 1: Reduce tidal volume to 6 ml/kg predicted bodyweight, as a first step towards protective lungventilation. Maintain PEEP 5.
 - b. Monitor 1,5 h.
 - c. Go back to conventional ventilator settings for 1,5 hours.
 - d. Decrease TV to 6 ml/kg predicted bodyweight and increase PEEP to 12 cm H₂O as in LPV.
 - e. Monitor 1,5 h.

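### The plan gives the conventional-phase ICP recorded before each intervention no role in the intervention 1 versus 2 comparison, so patient-specific drift would stay in its error

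*Combined protocol and SAP*

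**What the plan says.** The Intervention section gives the reason for crossing over: each patient's "outcomes on intervention 1 will be compared with her/his outcomes on intervention 2". Table 1 puts a phase at conventional settings directly before each intervention. The first is headed "Baseline (run-in period) 2 h" and the second "Baseline (wash-out) 1,5 h". Detailed conduct of the study confirms the second: "Go back to conventional ventilator settings for 1,5 hours".

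Outcome data exist for both phases. The observations section states "All primary and secondary outcome measurements will be recorded from minimum 2 hours before to 1 hours after intervention", and the rationale for monitoring adds "ICP will be measured continuously as part of routine monitoring by invasive ICP probe in the brain".

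On the model, Planned number of participants and statistical analysis says "Period effect, sequence effect and secondary outcomes will be analysed with linear mixed models". It bases the non-inferiority test on a confidence limit of a difference that it does not define. It names no covariate and does not mention the two conventional-phase values in connection with intervention 1 versus 2.

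**The concern.** A within-patient comparison removes stable differences between patients, and a period term removes drift shared by all. Neither removes drift that differs from patient to patient over the 3 h between the midpoints of the two interventions. Patients are recruited within 24 hours of brain injury, so such drift is plausible, although the documents give no rate for it. The change from run-in to wash-out is a direct record of each patient's own drift, already collected. If it is not used, the interval for the only randomised contrast (PEEP 12 versus 5 at the same tidal volume) may be wider than the data require, in a trial of 28 to 30 patients.

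The silence also leaves three analyses open once data are seen: unadjusted values, change from the preceding phase, and covariate adjustment. Their precision can differ a good deal.

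**Working it through.** **The plan's own figure.** Inputs from the sample-size paragraph: true difference 0, SD 4 mmHg, margin 3 mmHg, power 80%, significance level 0.025 (taken as one-sided).

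n = 2 × 4² × (1.960 + 0.842)² / 3² = 27.9, so 28.

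This is a cross-over total if 4 mmHg is the within-patient SD per period. The variance of the paired difference is then 2 × 16 = 32 (SD 5.66). The plan does not say which SD it means. With the t distribution, power is 77% at 28 patients and 80% at 30. The formula has no term for baseline adjustment.

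**Effect of adjustment.** Let Y1 and Y2 be a patient's ICP in the two interventions, B1 and B2 the ICP in the phases before them, and ρ = corr(Y1 − Y2, B1 − B2). With two sequences and one covariate, the variance relative to the unadjusted analysis is

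(1 − ρ²) × (n − 3)/(n − 4), and at n = 28 the second factor is 25/24 = 1.042.

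The documents do not give ρ, so two assumed models show a range. Both use whole-phase averages.

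*Model 1: serial correlation r between adjacent phases.* With the order B1, Y1, B2, Y2 and correlations r, r², r³ at lags 1, 2 and 3, ρ = (r − r³)/(2 − 2r²) = r/2.

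| r | ρ | Variance ratio, formula | Variance ratio, simulated |
|---|---|---|---|
| 0.5 | 0.25 | 0.98 | 0.97 |
| 0.7 | 0.35 | 0.91 | 0.91 to 0.93 |
| 0.9 | 0.45 | 0.83 | 0.83 to 0.85 |

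*Model 2: a linear slope for each patient, with the variance of Y1 − Y2 held at 32.* From the phase lengths in Table 1, the midpoints are 1.0, 2.75, 4.25 and 5.75 h, so the Y values are 3 h apart and the B values 3.25 h apart. For slope SD τ, drift contributes 9τ² to the variance of Y1 − Y2. The covariance with B1 − B2 is 9.75τ², and B1 − B2 has variance 10.56τ² + (32 − 9τ²).

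| τ (mmHg/h) | Drift share of 32 | ρ | Variance ratio, formula | Variance ratio, simulated |
|---|---|---|---|---|
| 0.5 | 7% | 0.08 | 1.04 | 1.02 to 1.03 |
| 1.0 | 28% | 0.30 | 0.95 | 0.95 to 0.96 |
| 1.5 | 63% | 0.65 | 0.60 | 0.59 to 0.60 |

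The worst case is ρ = 0, where the ratio is 1.042, a 4% loss at n = 28.

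**On the mmHg scale.** The unadjusted 95% half-width is 2.056 × 5.66/√28 = 2.20 mmHg. Under Model 1 it becomes about 2.18, 2.11 and 2.01 mmHg.

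**Change scores.** With equal variances their ratio is 2(1 − ρ). This exceeds 1 − ρ² by (1 − ρ)², so before the 1.042 factor change scores never do better than the covariate. Under Model 1 they raise the variance by 50%, 30% and 10%. They beat the unadjusted analysis only if ρ exceeds 0.5.

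**Carry-over into the wash-out.** Suppose intervention 2 differs from intervention 1 by δ, and a fraction c of that persists in B2 but not in Y2. The adjusted estimate then shifts by βcδ/2, where β is the slope on B1 − B2. With δ = 3 mmHg and c = 0.1 to 0.3, the shift is 0.04 to 0.20 mmHg under Model 1 (β = 0.25 to 0.45) and up to 0.28 mmHg for τ = 1.5 (β = 0.62). If PEEP raises ICP, the shift makes intervention 2 look slightly worse.

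**The case against.** A reader might infer that the plan has chosen raw values and excluded the baselines. It has not said so. The sentence in the Intervention section justifies the design and does not specify a model. The stated aim speaks of an ICP increase against conventional settings, so conventional-phase values must be used somewhere. What stands is that their role in intervention 1 versus 2 is unspecified.

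A reader might also infer that the trial loses power for its primary claim. The 3 mmHg margin is stated for protective versus conventional ventilation, where the conventional phase is the comparator and this adjustment does not apply. No margin is attached to intervention 2 versus 1. Moving from 77% to 78–84% power under Model 1 is therefore illustrative only.

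The largest gain is not a fair headline. With τ = 1.5, the drift SD between the first and last midpoints is 1.5 × 4.75 = 7.1 mmHg. That sits badly with patients who are deeply sedated, are excluded for ICP above 22 mmHg, and whose intervention is interrupted above that level. Elsewhere the gain is modest or slightly negative.

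Finally, the wash-out value arises after randomisation. Averaging the whole wash-out takes in the time straight after the first intervention, so adjustment could bias an estimate that was unbiased without it. That risk is real, but small in the cases worked, and a window late in the wash-out reduces it.

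**Conclusion.** The point holds as an omission that is cheap to repair. The plan records a conventional-phase ICP before each intervention and gives it no stated role in the intervention 1 versus 2 comparison, so an unadjusted analysis would keep patient-specific drift in its error. Order is randomised, so the loss is one of precision. Reading it as a bias, or as a flaw in the protective-versus-conventional test, goes beyond the documents.

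The simulated gain is about 3 to 17% of the variance for adjacent-phase correlation 0.5 to 0.9, or roughly 0.02 to 0.2 mmHg off a half-width of 2.20 mmHg. It is larger only under strong patient-specific drift. With almost none, adjustment costs about 2 to 4%. These figures assume 28 complete patients, equal phase variances (nearly so in the drift model), whole-phase averages and, for the mmHg values, a difference variance of 32. A shorter window may be noisier and change ρ.

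**What to change.** Add to the analysis section, before any outcome data are seen: for intervention 2 versus intervention 1 on ICP, regress each patient's period 1 minus period 2 value on sequence and on the difference between the two preceding conventional-phase values. Average each of these over the same fixed window at the end of the run-in and of the wash-out, for example the last 30 minutes. Such windows are centred at 1.75 and 4.75 h, 3 h apart like the intervention midpoints.

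State that simple change from the preceding phase will not be used for this contrast, and report the estimate without the covariate as a sensitivity analysis. State also that the adjustment does not apply to protective versus conventional ventilation. Extending it to PrX and other continuous outcomes is optional, since nothing here was calculated for them.

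The cost is a sentence or two and one degree of freedom, with no new data. The remaining risk is a small bias if the late wash-out still carries an effect of the first intervention. The sensitivity analysis would help to show it.
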